#### 17.1.3 Exploratory outcomes (Aim 1.3)

Compared to those receiving UC, patients randomized to also receive audio recordings (AUDIO) of clinic visits will report a greater self-management ability (PAM-SF) at 3 months. Despite their emerging use in primary care, we do not know the impact of audio recordings on patients' self-management. While we are not powered to test this primary hypothesis in the current project, our analytic strategy will enable us to gather crucial preliminary data on the potential effectiveness of AUDIO, preliminary data on mediators and moderators of the AUDIO intervention and refinements to the study protocol that may be required. Our overarching analytic strategy fully exploits the benefits of randomization by making minimalist assumptions and thereby is the most protected from bias due to erroneous modeling assumptions in comparing the AUDIO and UC groups. We later describe more nuanced analyses to allow for problems such as non-compliance, that can enable more statistical power by analyzing the outcome data as a longitudinal series (including control for the baseline value of the outcome) as opposed

PROTOCOL TITLE: *The impact of sharing audio recorded clinic visits on self-management in older adults: a multisite trial*  
to distinct cross-sections, as well as the analyses for the exploratory outcomes.

Because patients' AUDIO status varies within clinician, our statistical analysis of the PAM-SF score at 3 months' accounts for any dependence of the outcomes due to clinician within site effects. Therefore, to maximally benefit from the randomization of patients in physicians and generalize our results to a broader population, we will use a mixed-effect regression model of the form:

$$Y_{ij} = \beta_0 + \beta_1 Dartmouth_j + \beta_2 Vanderbilt_j + \beta_3 Audio_{ij} + \theta_j + \varepsilon_{ij} \quad (1)$$

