PROTOCOL TITLE: *The impact of sharing audio recorded clinic visits on self-management in older adults: a multisite trial*

patients assigned to UC who self-report that they recorded their visit and listened to the recording to estimate the quantity, the proportion of takers. Our estimator is based the relation with the just described proportions being substituted on the right-hand-side. This procedure corresponds to substituting the estimated value of  $\hat{\pi}$  for  $\pi$  in (1) as the resulting model can be seen as the second-stage of the two-stage least squares procedure adapted to a mixed-effect outcome model.

**17.1.5 Longitudinal use of recordings:** Another extension of our basic analysis will be to analyze the data from the two follow-up time periods (T1–T2) simultaneously using a longitudinal model. An advantage of this analysis is that it allows the form of the trajectory of the outcome variable over the follow-up time (e.g., is it constant, does it have an initial rise at T1 and then decline, does it grow with time) to be compared to a null model having a constant effect. This analysis provides a more powerful test of the effect of AUDIO than a cross-sectional comparison. In both the cross-sectional analyses of the outcome at a single follow-up time and the longitudinal analyses, the inclusion of the baseline (T0) value of the outcome variable as a covariate and/or making the difference in the outcome between  $T_k$  ( $k = 1, 2$ ) and T0 as the outcome are alternative analyses. Because our study is randomized, it is not necessary to include the outcome variable at T0 as a covariate from a bias standpoint, yet, doing so may improve the precision of our results. The chosen strategy will depend on the extent to which the baseline and follow-up outcomes cluster within patients. If clustering is high (e.g., intra-class correlation coefficient  $> 0.5$ ) we will include the T0 value of the outcome variable as a covariate.

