**17.1.6 Overall Predictiveness, Direction of Causality and Mediator Role of PAM-SF:** We first want to explore (i) whether self-management (PAM-SF), affects the exploratory (health) outcomes. We will then perform mediation analyses to decompose the overall effect of AUDIO into its indirect, or mediated, component that acts through PAM-SF and the direct component that affects the health outcomes independently of PAM-SF. With the availability of longitudinal data (1 week, and 3-months) we have the capability of regressing each health outcome on the lagged value of PAM-SF. The analyses in (i) will be performed by adding PAM-SF as a predictor variable and removing the intervention indicator variables from the statistical models used to analyze the health outcomes. Using the product of coefficients method, the effect of the intervention on the mediator is estimated in regression analyses like those described for the analysis of PAM-SF while the effect of the mediator (PAM-SF) on a given health outcome is estimated in a second regression model that also conditions on the AUDIO intervention. The product of the two coefficients corresponding to these effects is the mediation (or indirect) effect of the intervention on the outcome via the mediator while the coefficient for the AUDIO effect is in the latter regression and represents the direct effect of AUDIO. Standard errors will be evaluated using the bootstrap or the PRODCLIN program. A new body

PROTOCOL TITLE: *The impact of sharing audio recorded clinic visits on self-management in older adults: a multisite trial*

of research clarifies sequential ignorability and other assumptions required to obtain causal estimates of mediation effects in randomized studies. In addition to basic exploratory analyses, we will incorporate these new methods of performing mediation analysis into our analyses.

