where quantifies the extent to which the patient's HL modifies the effect of AUDIO on PAM-SF. A in (2) implies that the effect of AUDIO is lower in patients with high HL and higher in patients with low HL. We will also explore whether the impact of audio recording is greater for individuals at highest risk of poor self-management including those with moderate to severe depression and high disease burden. The variables described for the exploratory analyses will be analyzed using the model in (2) to form an analogous series of secondary and extended analyses for depression, anxiety, stigma and disease burden. Furthermore, we will examine whether 1) the presence of a caregiver or 2) sharing information (recording or AVS) with a caregiver moderates the impact of audio on PAM-SF. We will repeat these analyses to explore interaction effects by sex, race and ethnicity (**Sex as a Biological variable**), reporting interaction size and statistical significance.

**17.1.9 Appropriateness of Study Design:** The use of patient level randomization greatly

**PROTOCOL TITLE:** *The impact of sharing audio recorded clinic visits on self-management in older adults: a multisite trial*

simplifies the statistical analysis plan. Due to randomization, there is no need to include an elaborate array of predictors in the statistical model. Because patients are randomized the impact of clustering by clinician and site on standard errors will be minimal, however we will check to assure comparability of groups at baseline and control as needed. In fact, clinician and site act as blocks as we balance the proportion of patients assigned to AUDIO and UC within each of them to guard against the possibility that by chance any clinicians ended up with all patients being assigned to a given group and to maximally gain from the statistical efficiencies of a balanced design. That is, we essentially have a randomized block design. This allows analyses for site and clinician to be control variables whose inclusion sharpens the precision of our inferences, which are determined primarily off variation within clinician and site

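### Section 17.1.6 step (i) estimates what a non-randomized PAM-SF does to health outcomes without T0 PAM-SF, so stable patient differences can appear as an effect of activation

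*Combined protocol and SAP*

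**What the plan says.** Section 17.1.6, whose title includes direction of causality, opens with: "We first want to explore (i) whether self-management (PAM-SF), affects the exploratory (health) outcomes". It carries this out by "adding PAM-SF as a predictor variable and removing the intervention indicator variables from the statistical models used to analyze the health outcomes". It adds that, with data at 1 week and 3 months, "we have the capability of regressing each health outcome on the lagged value of PAM-SF".

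The models being modified come from section 17.1.3, where "we will use a mixed-effect regression model of the form" introduces model (1): site indicators, the AUDIO indicator and a clinician random effect. There are no patient covariates. Once AUDIO is taken out, PAM-SF is the only patient-level term left.

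Section 17.1.5 holds the only rule on baseline values. It argues that "Because our study is randomized, it is not necessary to include the outcome variable at T0 as a covariate from a bias standpoint", and then says that if clustering is high (the example is an intra-class correlation above 0.5) "we will include the T0 value of the outcome variable as a covariate". Section 17.1.9 gives the same reason for a short covariate list: "Due to randomization, there is no need to include an elaborate array of predictors in the statistical model".

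The mediation analysis that follows step (i) keeps AUDIO in its mediator-to-outcome regression and refers to sequential ignorability, but names no covariates. Table 1 marks PAM-SF at T0, T1 and T2. It marks ER visits and hospitalizations at one time only.

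**The concern.** Randomization protects the comparison of AUDIO with usual care. It gives no protection to a coefficient for PAM-SF, which patients bring with them. The reasons that sections 17.1.5 and 17.1.9 give for treating baseline adjustment as optional therefore do not carry over to step (i).

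The section 17.1.5 rule does not close the gap. In step (i) the outcome is the health outcome, so the rule can bring in the T0 health outcome but never T0 PAM-SF. Using T1 PAM-SF for a T2 outcome puts the two in time order, but does not remove differences between patients that were present before either was measured. The mediator-to-outcome regression likewise names no T0 PAM-SF.

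At stake is how the PAM-SF coefficient is read. Section 17.1.3 wants preliminary data on mediators, and the timeline in section 9.0 leads to an R01 submission. A PAM-SF coefficient that only reflects who the patients are could be carried forward as support for the causal chain from AUDIO through activation to health.

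**Working it through.** The plan states no effect size, power or sample size for step (i), so there is no figure to reproduce. The check asks what the step (i) coefficient would be if PAM-SF had no effect at all.

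**Inputs from the plan.** 90 patients (section 26.0); a T2 retention target above 70%, so about 0.70 × 90 = 63; the step (i) model; the section 17.1.5 rule.

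**Assumptions, not in the documents.** Within-arm variances of 1. PAM-SF and the outcome each correlate 0.6 with themselves over time. Stable traits carry a PAM-outcome correlation r of 0.2, 0.3 or 0.4 at every pair of times. AUDIO raises T1 PAM-SF and the T2 outcome by 0.3 SD each. With 1:1 allocation the arm indicator has variance 0.25, so AUDIO adds 0.25 × 0.3 × 0.3 = 0.0225 both to the variance of T1 PAM-SF and to its covariance with the T2 outcome. Clinician and site effects are left out.

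**Coefficient of T1 PAM-SF for the T2 outcome, true value 0.**

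| Terms besides PAM-SF | Formula | r = 0.2 | r = 0.3 | r = 0.4 |
|---|---|---|---|---|
| None: step (i), rule not triggered or no T0 outcome | (r + 0.0225)/1.0225 | 0.22 | 0.32 | 0.41 |
| AUDIO | r | 0.20 | 0.30 | 0.40 |
| T0 outcome: step (i), rule triggered | (0.4r + 0.0225)/(1.0225 − r²) | 0.10 | 0.15 | 0.21 |
| AUDIO, T0 outcome | 0.4r/(1 − r²) | 0.08 | 0.13 | 0.19 |
| AUDIO, T0 PAM-SF, T0 outcome | 0.4r/(1.6 − 2r²) | 0.05 | 0.08 | 0.13 |
| AUDIO, T0 PAM-SF, where no T0 outcome exists | 0.4r/(1 − 0.6²) | 0.13 | 0.19 | 0.25 |

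Worked example at r = 0.3. Step (i) alone: 0.3225/1.0225 = 0.32. With the rule triggered: 0.1425/0.9325 = 0.15. With all three terms: 0.12/1.42 = 0.08.

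Three things follow.

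- At a repeat correlation of 0.6 the section 17.1.5 example threshold of 0.5 is passed, so the third row is the plan's model wherever a T0 outcome exists. The first row applies where it does not, or where clustering is low.
- Comparing the first two rows, dropping AUDIO adds 0.01 to 0.02.
- The last row is only a guide for ER visits and hospitalizations, which are counts and would be fitted with a Poisson or negative-binomial model.

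**Separate check by simulation.** This used 3,000 runs per setting at n = 63 and n = 90, a single latent trait, PAM-SF repeat correlation of 0.5 to 0.7, a trait loading of 0.3 to 0.5 SD on the outcome, an outcome intra-class correlation of 0.6 and AUDIO effects of 0.3 SD. The false coefficient averaged 0.23 to 0.43 with PAM-SF alone (significant at 0.05 in 44 to 99% of runs), 0.11 to 0.22 with the T0 outcome added (18 to 68%), and 0.06 to 0.13 with AUDIO, T0 PAM-SF and the T0 outcome (7 to 20%). With no stable-trait confounding, leaving out AUDIO alone gave 0.02, with 5% of runs significant.

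**The case against.** The strongest reply is that the plan already holds part of the remedy. Where repeat values cluster strongly and a T0 outcome exists, the section 17.1.5 rule roughly halves the false coefficient (at r = 0.3, from 0.32 to 0.15). A reader might infer that 0.22 to 0.41 SD describes step (i) throughout. The documents do not support that; it describes step (i) only when the T0 outcome is absent. Section 17.1.5 also lists change from T0 as an alternative outcome. That would largely cancel a difference equally present at T0 and T2, but the plan states no condition that selects it.

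A reader might also infer that removing AUDIO is the main fault. The table shows that it is minor, and restoring AUDIO alone would fix almost nothing.

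Nor does the plan shut out T0 PAM-SF everywhere. In the AUDIO-to-PAM-SF regression PAM-SF is the outcome, so the same rule can bring it in. The mediator-to-outcome regression keeps AUDIO, and the section undertakes to use newer causal mediation methods. The gap there is an unnamed covariate set rather than an unrecognized assumption.

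Finally, this is exploratory work in a pilot that disclaims power (section 17.1.10), so it would be too much to say that the trial will conclude that activation improves health. All of this stands as a limit on size and weight. None of it puts T0 PAM-SF into step (i) or into the mediator-to-outcome regression.

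**Conclusion.** The point holds in a limited form. Step (i) puts a causal question to a non-randomized predictor, relies on a baseline rule justified by randomization, and names no T0 PAM-SF. Under the assumptions above, a null PAM-SF would show a coefficient of about 0.10 to 0.21 SD where the T0 outcome is included and 0.22 to 0.41 SD where it is not. Full adjustment brings this to 0.05 to 0.13 SD, which reduces the bias without removing it. That remainder is why the result should be called an association even after adjustment.

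The sizes depend on correlations that the documents do not give; the gap in the text does not. What is affected is the interpretation of an exploratory coefficient. The feasibility and acceptability endpoints do not depend on it.

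**What to change.** In section 17.1.6:

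- In step (i) and in the mediator-to-outcome regression, always include T0 PAM-SF and, where it is collected, the T0 value of the outcome, whatever the intra-class correlation.
- Keep the AUDIO indicator in step (i).
- State that T1 PAM-SF is the predictor of the T2 outcome, rather than leaving the lag as an option.
- Report the step (i) PAM-SF coefficient as an association, and say that for outcomes with no T0 value, such as ER visits and hospitalizations, the adjustment is weaker.

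The cost is a change of wording and 2 to 3 degrees of freedom out of roughly 63 to 90 patients: one each for T0 PAM-SF, AUDIO and, where available, the T0 outcome. No new data collection is needed, because PAM-SF is already measured at T0 and T1 and the T0 outcome is asked for only where it exists.

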## 4.0 Study Endpoints\*

### 4.1 Primary endpoint

The primary endpoints of this pilot trial are:

1) Feasibility: We will determine the optimal strategy to achieve a high retention rate and adherence to the study protocol. We will also assess retention rates (proportion of included patients completing T2 follow up; we will target >70%), fidelity to the study protocol (Borrelli et al criteria; we will target >90%) and the Feasibility of Intervention Measure (FIM, 4 items, see Appendix 1. 3-month Follow Up Assessment (T2); we will target an average score of >3).

2) Acceptability: We will determine the acceptability of the AUDIO intervention and study protocol by assessing the proportion of patients and clinicians who agree to take part in the project and proportion of patients who listen to the recording. Our primary indicator of acceptability will be the recruitment of 108 participants (N=30 patients and 6 clinicians per site) over our planned data collection period of six months. We will determine the listening rates (we will target >70%): this will include the proportion of patients in the intervention arm that log in to the online system and listen to (and how often) the recording. We will also document the number of patients who share or report sharing the recording and caregivers who access the recording. Participants will complete the Acceptability of Intervention Measure (AIM, 4 items, see Appendix 1. 3-month Follow Up Assessment (T2); target an average score of >3).

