**5.1.1 Listening regime:** We will instruct patients to listen to their most recent recording both within 24 hours after their visit (as a means to reinforce and recall self-management information discussed), at one week (to reinforce learning) and within three days prior to their next visit (to identify information that needs clarification orgaols of care they would like to raise with their clinician). A reminder to listen to the recording will be sent to patients by email and/or text message (Appendix 24. Patient HealthPAL Reminder Emails). Patients will have the option of providing the contact information (email) of a family member, or caregiver who typically assists, or is involved in their care, and the study team will send this person access to the recording via the website.

**5.1.2 Recording future visits:** The RA will review the EMR of participants and document in REDCap scheduled patient visits (up to 6 months from recruitment). For patients in the AUDIO group, the RA will also attend each visit and assist with recording as described above, and administer the IPC survey post visit. While patients in the UC group have no further in clinic procedures following baseline assessment, we will plan to attend these visits when possible and offer participants the opportunity to complete the IPC survey post visit. We anticipate that patients will have one additional scheduled clinic visit over the 3-month period based on the average number of visits of these types of patients estimated from EMR data at each clinic site in 2017. We will neither record nor conduct follow-up assessments of unscheduled/urgent or acute visits so as to

PROTOCOL TITLE: *The impact of sharing audio recorded clinic visits on self-management in older adults: a multisite trial*  
minimize burden on both participants and study staff.

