**Assessments:** A trained RA will collect data (**T0**= Baseline Assessment) by electronic tablet or by paper form if preferred by the patient prior to the visit. Patients who complete eConsent can also complete the baseline assessments via REDCap prior to the clinic visit. The PHQ-8 and GAD-7 will be administered after the clinic visit. Follow up is planned by email (Appendix 25 for the REDCap Survey Template) or telephone at **T1**= one week, **T2**= three months. For T1, the allowable window is up to two weeks from the scheduled timepoint. For T2, the allowable window is up to three weeks from the scheduled timepoint. Deviations from the follow up strategy (e.g., a patient who completes an assessment outside of the planned follow up window) will be reported to the IRB. No participant identifiers will be included on the labeling of study data. Study Unique ID code numbers instead of names will be used on participant materials, data and data-collection instruments to minimize risks regarding breach of confidentiality.

Patients will receive a printed schedule of follow-up assessments, tailored to times and days convenient to them.

Outside of the standard study follow up assessments, the patient will be met in clinic or contacted by email or telephone one week from any scheduled visit with a participating clinician to assess intervention use (AVS or AUDIO) and interpersonal processes of care (IPC) survey (immediately following the clinic visit, or within 1 week of the visit by email or telephone with the RA).

**6.4 Outcomes:** Our primary and exploratory outcome measures are outlined in Section 4.2 Table 1.

**6.4.1 Covariates:** Demographic information (age, sex, race, ethnicity, language used at home, educational attainment using categories from the 2016 American Community Survey) will be collected by the RA through patient report at enrollment. We will document if a caregiver (a support person, family member or friend) is present at the visit. We will collect demographic and practice information about participating clinicians including their age, sex, race, ethnicity and years in practice. The following covariates will be examined in our exploratory moderator analysis:

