**Health literacy:** We will use two assessments, the 3-item validated Brief Health Literacy Scale (BHLS) and the 18-item validated Short Assessment of Health Literacy (SAHL-E). Both scales are validated in English and Spanish. Scores on the BHLS range between 3 and 15, with higher scores indicating higher subjective health literacy. Scores on the SAHL-E range from 0 – 18; ≤14 is considered low health literacy

**Disease burden:** The Charlson Comorbidity Index (CCI) using EMR data. Each condition is assigned a score, based on risk of death, which is summed, with higher scores indicating higher disease burden.

PROTOCOL TITLE: *The impact of sharing audio recorded clinic visits on self-management in older adults: a multisite trial*

**Depression:** The eight-item PHQ-8 validated in both English and Spanish. Scores range from 0 – 24; a score  $\geq 10$  indicates major depression, and a score of  $\geq 20$  indicates severe major depression.

**Anxiety:** The seven-item GAD-7 validated in both English and Spanish. Scores of 5, 10, and 15 represent cut points for mild, moderate, and severe anxiety, respectively.

**Diabetes Stigma:** The comprehensive diabetes stigma scale (CSSS-15) is a validated 15-item assessment of diabetes-related stigma. It is composed of four subscales: (1) enacted (0-6), (2) perceived (1-5) and (3) self-stigma(1-5), and (4) concealment (1-5). Subscale scores are means of responses, and an overall score is the sum of all items (11-96).

**Stigma of Chronic Illness.** The Stigma Scale for Chronic Illness (SSCI-8) is validated, eight-item assessment of stigma related to chronic disease. It is scored from 8 (low stigma) to 40 (high stigma), and can be converted on to a standardized T-distribution score with a mean of 50 and standard deviation of 10.

**Audio & AVS Use:** Intervention use by patients will be monitored within the HealthPAL application: we can determine when a 1. patient logs into their account; 2. listens to a recording; and 3. shares the recording. AVS use will be assessed at standard outcomes assessments and one week from scheduled clinic visit during the data collection period: we will determine whether the patient reviewed the AVS and whether they shared it.

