## 22.0 Consent Process

### 22.1 Consent Process (Aim 1 Trial)

#### 22.1.1 Patients (Aim1)

**eConsent:** A link to the consent form will be sent via REDCap immediately after the screening phone call with the RA to eligible interested patients willing to complete eConsent. The eConsent will consist of the same, age-appropriate materials as in-person consent (described below). Patients will be instructed to review the eConsent. Participants will have the ability to move forward or backward on the eConsent form as needed prior to completing consent. A short quiz to confirm patient understanding of the project will be completed electronically as part of the eConsent process - this is a common step in eConsent processes (Appendix 23. eConsent Comprehension Quizzes). Contact information will be available to participants should they have further questions or points needed to be clarified with the study team. Participants will also have the option to provide the name and email of a friend or family member who they involve in their care and would be willing to share their recording with. Those who complete eConsent will leave a digital signature; they will be emailed a copy of their signed eConsent form and will also be offered a mailed paper copy of the consent form. Participant and study staff signatures on the eConsent may have different dates, as participants may sign during non-business hours. Study staff will sign the eConsent electronically as soon as feasible after participant completion. Participants will also receive an email asking them to attend clinic 30 minutes early on the day of the research if they would prefer to complete pre-visit surveys in person rather than electronically. On the day of the visit, a member of the research team will meet with the participant, either in person or by telephone/web conference, and proceed with study procedures.

**In-person consent:** For participant who prefer to complete consent in clinic, they will be met by the RA in the clinic waiting room. A member of the registration staff may also receive a list of patients who have agreed to learn more about the project, to facilitate a warm hand-off of patients to the RA. Patients will join the RA in a private room/area where they will confirm inclusion and exclusion criteria with the patient. This will be done using a short, standardized screening form. Once it is determined that the

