**Family members & caregivers/companions (Aim1)**. As patients are the focus of the project we will initially identify, inform and consent patients. To be eligible, patients must meet inclusion / exclusion criteria and be able to provide consent independently. If a family member is present, we will provide them with study information upon patient consent, including whether the patient has been randomized to the AUDIO arm and explain that patients in the AUDIO arm will have their scheduled visits with this clinician audio recorded and shared for the patient's personal use during the study period (3 months). As such the caregiver or family member will be aware that recording is taking place at the visits. At each visit, the research assistant will remind accompanying caregivers or family members that the patient has consented for the visit to be audio recorded. It is important to note that patients will always be able to pause or stop a recording of the visit, and we plan to document such instances on our fidelity checklist. Family or other members may elect to not be in the visit room, and this will be documented. This approach was developed after careful discussion with clinic risk management, clinicians, patients and caregiver partners. It also reduces selection bias issues as the alternative approach of consenting accompanying family members or caregivers may impact the patient's decision to participate or not. This strategy has also been approved and successfully used in a prior project by the Dartmouth IRB (STUDY00031211).

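### Section 17.1.8 tests sharing with a caregiver, a behaviour that follows randomisation and differs by arm, as a moderator of the AUDIO effect (minor; exploratory analyses only)

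*Combined protocol and SAP*

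**What the plan says.** Section 17.1.8 adds a moderator and its interaction with AUDIO to model (1). Besides health literacy, depression, anxiety, stigma, disease burden, sex, race and ethnicity, it asks whether "the presence of a caregiver or 2) sharing information (recording or AVS) with a caregiver moderates the impact of audio on PAM-SF".

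On sharing:
- Section 6.1 gives recordings to the AUDIO arm only.
- Section 5.1.1 lets patients name a caregiver, and then "the study team will send this person access to the recording via the website". No such step is described for the AVS.
- Sections 4.1 and 17.1.2 count "the number of patients who share or report sharing the recording and caregivers who access the recording". Section 6.4.1 adds HealthPAL monitoring of shares.
- For the AVS, Section 6.4.1 relies on assessments during follow-up: "we will determine whether the patient reviewed the AVS and whether they shared it".

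On caregiver presence, Section 6.4.1 says "We will document if a caregiver (a support person, family member or friend) is present at the visit". The family and caregiver paragraph of Section 22.1 gives companions study information "including whether the patient has been randomized to the AUDIO arm", and adds: "Family or other members may elect to not be in the visit room, and this will be documented".

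On baseline, Table 1 and Section 6.0 define T0 as pre-visit, and Section 6.1 reveals allocation once T0 is complete. The study procedures in the same section let the pre-visit surveys be done after the visit when time is short. Sections 6.1 and 6.3 place PHQ-8 and GAD-7 after the visit, while Table 1 marks them at T0.

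**The concern.** A moderator analysis keeps the protection of randomisation only if the moderator could not have been affected by allocation. Sharing can be. An AUDIO patient who shares has passed on a recording, perhaps through study staff; a usual-care patient who shares has passed on a summary unaided. The two groups of sharers are selected by different processes, and so are the two groups of non-sharers. If more activated patients share more readily in one arm than in the other, an interaction appears even when AUDIO works equally for everyone.

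Section 17.1.3 wants preliminary moderator data for a later trial. A finding that AUDIO works in those who share could shape that trial's eligibility or intervention when it only reflects who shares in each arm. Section 17.1.6 discusses the causal assumptions behind mediation; Section 17.1.8 carries no comparable caution.

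Caregiver presence raises a lesser question. It is a baseline trait if recorded before allocation, but not if it means being in the room after the companion has learned the arm.

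**Working it through.** The plan states no figure for this point, so there is none to reproduce. All inputs below are assumptions except n = 90 patients (Section 26.0), the 70% retention threshold (Section 4.1; 0.70 × 90 = 63), and 47% sharing (16 of 34 interviewees in Section 3.2.2, used only for scale).

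**Sharing.** Let U be activation, N(0,1), with correlation r to the outcome (SD 1). The true AUDIO effect is 0.30 for everyone. In each arm logit Pr(share) = a + bU, with a set so that 47% share in AUDIO and 20% in usual care. Let m1 and m0 be the means of U among sharers and non-sharers (80-node Gauss-Hermite quadrature). Then:

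- apparent effect in sharers = 0.30 + r(m1 AUDIO − m1 UC)
- apparent effect in non-sharers = 0.30 + r(m0 AUDIO − m0 UC)
- false interaction = the first minus the second

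Example, slopes 1.0 in AUDIO and 0 in UC: the AUDIO means are 0.438 and −0.389, and both UC means are 0. The interaction is r × 0.827, which is 0.58 at r = 0.7 and 0.17 at r = 0.2.

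| Slope b, AUDIO / UC | Sharers, r = 0.7 | Non-sharers, r = 0.7 | Interaction, r = 0.7 | Interaction, r = 0.2 |
|---|---|---|---|---|
| 1.0 / 0 | 0.61 | 0.03 | +0.58 | +0.17 |
| 0.5 / 0 | 0.48 | 0.15 | +0.33 | +0.09 |
| 0.5 / 0.25 | 0.34 | 0.18 | +0.16 | +0.04 |
| 0.5 / 0.5 | 0.21 | 0.21 | −0.01 | 0.00 |
| 0.5 / 0.75 | 0.09 | 0.24 | −0.15 | −0.04 |
| 0.25 / 0.5 | 0.12 | 0.29 | −0.16 | −0.05 |
| 0 / 0.5 | 0.03 | 0.37 | −0.34 | −0.10 |
| 0 / 0 | 0.30 | 0.30 | 0 | 0 |

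At r = 0.5 the extremes are +0.41 and −0.24. With equal slopes and 47% sharing in both arms, both strata return 0.30.

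Interaction SE, n = 90 (45 per arm): √[1/(0.47×45) + 1/(0.53×45) + 1/(0.20×45) + 1/(0.80×45)] = 0.48, with about 9 usual-care sharers. At n = 63 it is 0.57, with about 6. Simulation gives 0.49 and 0.59. The largest false interaction is therefore 0.58/0.49 = 1.2 SE at n = 90, and the largest negative one 0.34/0.49 = 0.7 SE.

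**Caregiver presence, only if it means in the room.** With 40% accompanied and 10% to 20% of AUDIO companions staying out, the false interaction is 0 if leaving is unrelated to activation, and 0.05 to 0.18 SD in either direction if related (slope 0.5 to 1.0, r = 0.7).

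**Late T0.** Let a fraction f be completed late, with an AUDIO-only shift d in the T0 score and T0-to-T2 correlation ρ. Bias is −f·d·ρ in the adjusted model and −f·d for a change score. At f = 0.25, d = 0.2, ρ = 0.7 these are −0.035 and −0.05 SD. If both arms shift equally, both are zero. The SE is √[4(1−ρ²)/n] adjusted and √[8(1−ρ)/n] for change. Over ρ = 0.7 to 0.5 and n = 90 to 63 these run 0.15 to 0.22 and 0.16 to 0.25. In simulation at the worst case (n = 90), root mean squared error of the adjusted estimate was 0.155 keeping late values, 0.161 imputing them and 0.174 excluding them.

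**PHQ-8 and GAD-7 as a cut-off moderator.** With 20% above the cut-off, correlation −0.4 with the outcome, and AUDIO-related shifts of up to 0.2 SD in either direction (or −0.4 SD in high scorers only), the false interaction is −0.07 to +0.03 SD, against an SE of 0.52 to 0.64.

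**The case against.** The strongest reply is that these analyses are exploratory, admittedly unpowered and mainly descriptive (Sections 17.1 and 17.1.10), so a clear non-causal label would be enough. Much of this stands. It is why the point is minor, and a labelled association is an acceptable fallback. Low power does not, however, turn the contrast into effect modification, and a point estimate can be carried forward whatever its SE.

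The size is also open to challenge. Every bias scales with the assumed correlation, and +0.58 needs strong selection in AUDIO and none in usual care. That is correct, hence the range.

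On T0, late completion can be read as a stated exception to a general rule. The remaining gap is that Section 6.1 does not say when such a patient is allocated, although an in-person AUDIO recording starts before the clinician enters (Section 5.2). Nor can online or telephone completion be required of everyone, because Sections 6.1 and 6.3 tie completion before the clinic visit by those routes to eConsent. Post-visit PHQ-8 and GAD-7 are deliberate and disclosed, so only their label is at issue.

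A reader might infer that caregiver presence is also invalid as a moderator. The documents do not establish that: staying out of the room is recorded separately, and presence could be noted before allocation.

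**Conclusion.** Section 17.1.8 is wrong as written on sharing: the interaction and the within-stratum effects are not protected by randomisation. That conclusion is textual and does not depend on the simulation.

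The size does depend on assumptions. A false interaction could plausibly lie between about −0.34 and +0.58 SD at correlation 0.7, or −0.10 and +0.17 SD at 0.2, usually within about one SE. When slopes are equal but sharing rates differ, the interaction nearly vanishes while both stratum effects can still be off (0.21 instead of 0.30).

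A reader might infer that the trial will falsely show benefit in sharers. The documents do not support this, because the error can go either way and can be nil. Nor do they support a wider charge: the feasibility and acceptability endpoints, the unadjusted PAM-SF comparison, and the disease-burden, sex, race and ethnicity moderators are unaffected.

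The T0 and PHQ-8/GAD-7 items are wording and labelling notes with negligible effect on results.

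**What to change.** **Section 17.1.8, sharing.** Drop sharing as a moderator and report it descriptively by arm, or at most as an explicitly non-causal association. The data are already planned in Sections 4.1, 6.4.1 and 17.1.2.

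**Caregiver moderator, if wanted.** Use a caregiver named, or attendance recorded, before allocation. Section 22.1.1 already provides at eConsent that "Participants will also have the option to provide the name and email of a friend or family member"; ask the same at in-person consent and record a no as an answer. Define caregiver presence as this pre-allocation record and report in-room presence descriptively.

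**T0 wording (Sections 4.2, 6.0 and 6.1).** State that allocation occurs before the visit, that T0 scales are completed before allocation where possible, and that late completion is a time-stamped exception reported by arm. Keep late values in the main T0-based analyses and add one sensitivity analysis that excludes or imputes them.

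**PHQ-8 and GAD-7.** Leave the timing alone. Label their T0 values and moderator results as post-allocation measures in Table 1 and Section 17.1.8.

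**Cost.** Small wording changes, a REDCap time stamp, one question at in-person consent and one sensitivity analysis. The planned sharing interaction is lost.
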